Protocol for non-interventional studies based on existing data

Document Number:	c26865718-02
BI Study Number:	0205-0542
BI Investigational Product(s):	Spiriva® HandiHaler® & Respimat® (Tiotropium)
Title:	Non-interventional study to compare effectiveness of LAMA to fixed dose combination of inhaled corticosteroid and long-acting beta agonists (ICS/LABA) in patients with chronic obstructive pulmonary disease (COPD) based on existing data
Protocol version identifier:	Version 1
Date of last version of protocol:	8 Apr 2020
PASS:	No
EU PAS register number:	32329
Active substance:	Tiotropium Bromide Monohydrate
Medicinal product:	Spiriva® HandiHaler®, Respimat®
Product reference:	Ba 679 BR
Procedure number:	
Joint PASS:	No
Research question and objectives:	
A study to compare the occurrence of several outcomes after initiation of ICS/LABA therapy with their occurrence after initiation of LAMA therapy in COPD will be conducted. More specifically, the objective is to compare:
 
 - Comparison of pneumonia incidence in COPD patients using LAMA and ICS/LABA - Comparison of exacerbations frequency and rate in COPD patients using LAMA and ICS/LABA - Comparison of time to start triple combination therapy (time from initial 'LAMA mono' or ICS+LABA' to 'LAMA+LABA+ICS' combination) in COPD patients using LAMA and ICS/LABA - Comparison of health care utilization: Medical cost / No. of prescriptions, visits and hospitalizations

	
- Ly Expected adverse events after long term use of ICS : recurrence of TB (tuberculosis), incidence of NTM(Non-tuberculosis Mycobacteria) lung disease- Comparison of all-cause mortality differences in COPD patients using LAMA and ICS/LABA- Comparison of lung cancer incidence in COPD patients using LAMA and ICS/LABA
Country of study:	South Korea
Author:	[REDACTED] [REDACTED] [REDACTED]
Marketing authorisation holder(s):	[REDACTED] [REDACTED] [REDACTED] [REDACTED]
MAH contact person:	[REDACTED] [REDACTED] Phone: [REDACTED]
In case of PASS, add: <EU-QPPV:>	NA
In case of PASS, add: <Signature of EU-QPPV:>	NA
Date:	3 Jun 2020
Page 2 of 31	
Proprietary confidential information © 2022 Boehringer Ingelheim International GmbH or one or more of its affiliated companies. All rights reserved. This document may not - in full or in part - be passed on, reproduced, published or otherwise used without prior written permission	

2. LIST OF ABBREVIATIONS

AE	Adverse Event
CI	Confidence Interval
[REDACTED]	[REDACTED]
[REDACTED]	[REDACTED]
SAE	Serious Adverse Event
SAP	Statistical Analysis Plan
IEC	Independent Ethics Committee
IRB	Institutional Review Board
FDC	Fixed dose combination
MD	Medical doctor
HR	Hazard Ratio
SPC	Summary of Product Characteristics
TMM	Team Member Medicine
TMW	Trial Medical Writer
TBD	To Be Decided
[REDACTED]	[REDACTED]
ER	Emergency Room

4. ABSTRACT

Name of company: Boehringer Ingelheim			
Name of finished medicinal product: Spiriva® HandiHaler®, Respimat® (Tiotropium Bromide Monohydrate)			
Name of active ingredient: Tiotropium Bromide Monohydrate			
Protocol date: 3 Jun 2020	Study number: 0205-0542	Version/Revision: 1	Version/Revision date:
Title of study:	Non-interventional study to compare effectiveness of LAMA to fixed dose combination of inhaled corticosteroid and long-acting beta agonists (ICS/LABA) in patients with chronic obstructive pulmonary disease (COPD) based on existing data		
Rationale and background:	
According to the GOLD guidelines, ICS use should be limited in scope to a small portion of COPD patients³. However, ICS is largely overprescribed in clinical practice, regardless of COPD severity and exacerbation risk⁴⁻¹⁰.
 
Even though Regular maintenance ICS therapy is associated with an increased risk of pneumonia, physicians do not change their current practice easily^{1,3,11}. Therefore, we need a supportive data to niche on the proper role of ICS in treating COPD patients
 
Tiotropium has been the No. 1 COPD maintenance therapy over the past 12 years in Korea and it is time to a timely review its clinical benefit in the real world setting through cumulated data.
 
Spiolto Respimat® (it is called as Vaheleva® Respimat® in Korea) data has not been cumulated enough to be compared with ICS/LABA because its launch date in Korea was April 1st 2016.
		
Research question and objectives:	
A study to compare the occurrence of several outcomes after initiation of ICS/LABA therapy with their occurrence after initiation of LAMA therapy in COPD will be conducted. More specifically, the objective is to compare:
 
- Comparison of pneumonia incidence in COPD patients using LAMA and ICS/LABA (pneumonia relative hospitalization and death will be seen as sub-analysis)- Comparison of exacerbations frequency and rate in COPD patients using LAMA and ICS/LABA- Comparison of time to start triple combination therapy (time from initial 'LAMA mono' or ICS+LABA' to		

Name of company: Boehringer Ingelheim					
Name of finished medicinal product: Spiriva® HandiHaler®, Respimat® (Tiotropium Bromide Monohydrate)					
Name of active ingredient: Tiotropium Bromide Monohydrate					
Protocol date: 3 Jun 2020	Study number: 0205-0542	Version/Revision: 1	Version/Revision date:		
		
‘LAMA+LABA+ICS’ combination) in COPD patients using LAMA and ICS/LABA
 
 - Comparison of health care utilization: Medical cost / No. of prescriptions, visits and hospitalizations - Expected adverse events after long term use of ICS : recurrence of TB and incidence of NTM lung disease - Comparison of all-cause mortality differences in COPD patients using LAMA and ICS/LABA 
Comparison of lung cancer incidence in COPD patients using LAMA and ICS/LABA
			
Study design:	Non-interventional, Single-country study based on existing data from medical records of COPD patients treated with LAMA or fixed dose combination of ICS/LABA				
Population:	
 • Inclusion criteria 
 - Diagnosed with COPD [based on ICD-10 code (J43.x-44.x except J430), as the primary or within the forth secondary diagnosis and initiated LAMA or ICS/LABA more than twice a year from Jan 1, 2005 to Apr 30 2016]. - Age>55 years old as of 2005 when enroll started • Exclusion criteria 
 - Prescription history with any long acting and short bronchodilator for maintenance therapy (the patient should be inhaler naïve) from 2002 to 2005 - Prescription history with Leukotriene receptor antagonist(LTRA) or ICS - Prescription history of LABA/LAMA FDC 
Patients with lung cancer, IPF, ILD or lung transplantation at the time of COPD diagnosis
				
Variables:	Detailed definitions of variables that will be derived for statistical analyses and summaries will be included in the Statistical Analysis Plan (SAP).				

Name of company: Boehringer Ingelheim			
Name of finished medicinal product: Spiriva® HandiHaler®, Respimat® (Tiotropium Bromide Monohydrate)			
Name of active ingredient: Tiotropium Bromide Monohydrate			
Protocol date: 3 Jun 2020	Study number: 0205-0542	Version/Revision: 1	Version/Revision date:
Data sources:	Korea National Health Insurance claim data & mortality data from the Bureau of Statistics from Jan 2005 to Apr 2016.		
Study size:	At least 10,000 total. At least 5,000 for each arm.		
Data analysis:	All analyses will be performed with SAS and R. All variables will be summarized descriptively through displays of mean(\pm standard deviations), median, and ranges for continuous variables, and frequency distributions of categorical variables. To address the imbalance of potential confounders between LAMA ICS/LABA groups, we matched treatment groups using propensity scores estimated as by multiple logistic regression analysis based on age, sex, socioeconomic status, Charlson Comorbidity Index, and asthma, and history of COPD exacerbation. Cox proportional hazards regression analyses will be used to estimate hazard ratios (HRs) and 95% confidence intervals (95% CIs) for all outcomes. For (possibly) repeating events (such as exacerbation event) additionally a Poisson regression model will be fitted for the number of events (taking into account the matching). Detailed methodology for summary and statistical analyses of data in this study will be documented in an SAP.		
Milestones:	Start of data collection in 2020 April 15 End of data collection in 2020 Dec 31 Start of data analysis in 2021 Jan 1 End of data analysis in 2021 Dec 31 Final report of study results expected in 2022 Aug		

5. AMENDMENTS AND UPDATES

Number	Date	Section of study protocol	Amendment or update	Reason
1	8 Apr 2020	Milestones	Update	Specific dates have been added for the study timeline
2	3 Jun 2020	Milestones	Update	Dates have been added for the study timeline

6. MILESTONES

Milestone	Planned Date
Registration in the EU PAS register	15 Nov 2019
Start of data collection	15 Apr 2020
End of data collection	31 Dec 2020
Final report of study results	30 Aug 2022

7. RATIONALE AND BACKGROUND

According to the GOLD guidelines, ICS use should be limited to a small portion of COPD patients³. However, ICS are largely overprescribed in clinical practice, regardless of COPD severity and exacerbation risk⁴⁻¹⁰. Even though maintenance ICS therapy is associated with an increased risk of pneumonia, physicians do not change their current practice easily^{1,3,11}. Therefore, we need a supportive data on the proper role of ICS in treating COPD patients.

Tiotropium has been the No. 1 COPD maintenance therapy over the past 12 years in South Korea and a timely review its clinical benefit in the real world setting through cumulated data.

Spiolto Respimat® has not been accumulated enough data to be compared with ICS/LABA because its launch date in Korea was April 1st 2016.

8. RESEARCH QUESTION AND OBJECTIVES

In COPD patients, long-term use of ICS is reported to be linked to an increase in the rate of serious pneumonia¹. A study to compare the occurrence of several outcomes after initiation of ICS +LABA therapy with the occurrence after initiation of LAMA therapy in COPD will be conducted. More specifically, the objective is to compare:

- Comparison of pneumonia incidence in COPD patients using LAMA and ICS/LABA
- Comparison of exacerbations frequency and rate in COPD patients using LAMA and ICS/LABA
- Comparison of time to start triple combination therapy (time from initial 'LAMA mono' or ICS+LABA' to 'LAMA+LABA+ICS' combination) in COPD patients using LAMA and ICS/LABA
- Comparison of health care utilization: Medical cost / No. of prescriptions, visits and hospitalizations
- Expected events after long-term use of ICS: osteoporosis, bone fracture, diabetes mellitus, cataracts and recurrence of tuberculosis, Non-tuberculosis Mycobacteria lung disease
- Comparison of all-cause mortality differences in COPD patients using LAMA and ICS/LABA
- Comparison of lung cancer incidence in COPD patients using LAMA and ICS/LABA

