9.2 SETTING

The study will be conducted in a general practice setting, Korea National Health Insurance claim data & mortality data from the Bureau of Statistics, which includes computerized medical records of more than half million patients in South Korea. The maximal observation period will be from Jan 2005 to Apr 2016.

- Inclusion criteria
 - Diagnosed with COPD [**based on ICD-10 code(J43.x-44.x except J430), as the primary or within the fourth secondary diagnosis and initiated LAMA or ICS/LABA more than twice a year from Jan 1, 2005 to Apr 30 2016**].
 - Age >55 years old as of 2005 when enroll started
- Exclusion criteria
 - Prescription history with any long acting bronchodilator for maintenance therapy (the patient should be inhaler naïve) from 2002 to 2005.
 - Prescription history with ipratropium bromide
 - Prescription history with Leukotriene receptor antagonist(LTRA) or ICS
 - Prescription history of LABA/LAMA FDC
 - Patients with lung cancer, IPF, ILD or lung transplantation at the time of COPD diagnosis

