9.7.1 Analysis Dataset : Patients selection

The matching between LAMA[Spriva® HandiHaler® Respimat® (Tiotropium Bromide Monohydrate)] and ICS/LABA are performed by sex, age category (5 year spans above 55 years), years since diagnosis of COPD, as available in the database, and propensity score.

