9.7.1.1 Propensity score methodology

The propensity score will model the likelihood among COPD patients of receiving LAMA and ICS/LABA. The model for the propensity score will to the extent possible include the following elements:

- 1) Age and sex
- 2) Socioeconomic status (e.g. income, educational level, single living)
- 3) History of COPD exacerbation
- 4) Charlson Comorbidity Index
- 5) History of asthma

A logistic regression analysis will be performed on the identified COPD patients where treatment with LAMA and ICS/LABA groups is the dependent, dichotomous variable and the independent variables are listed above (age, sex and history of COPD exacerbation et al.). Based on this analysis, the propensity score is calculated for each patient. For subgroup analyses, PS matching and evaluation of its success, as presented below, will be re-done as covariate balance is not automatically maintained in sub-cohorts.

Smoking may be an important confounder in COPD but smoking status is usually not available in the databases at all. If smoking status is confirmed to be available, the data will be analysed with and without smoking status included in the model and the magnitude of the confounding effect assessed (sensitivity analysis).

PS matching will be done in a 1:1 ratio using the nearest-neighbor algorithm, using calipers of width equal to 0.2 of the standard deviation of the logit of the PS (matches of the main exposure sub-cohort and the comparator sub-cohort are formed if the caliper width is not exceeded for the logit of PS). For LAMA-exposed patient to ICS/LABA-exposed patients will be selected within the same matching interval of the propensity score. The distribution of propensity scores will be examined between LAMA-exposed and eligible ICS/LABA-exposed. In the matching procedure, matched comparator sub-cohort patients (ICS/LABA) will be removed from the pool of eligible patients among the comparator sub-cohort so that a matched patient is no longer available for consideration as a potential match for another exposed patient.

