9.7.2 Main analysis

For the primary effectiveness outcomes incidence rates (events per 1,000patients-years) with corresponding 95% confidence intervals (CI) will be calculated. This will be evaluated by a matched Cox proportional hazards regression model for counting processes, which allow the follow-up time to be divided into several periods and therefore control for baseline and time-dependent covariates, using the full observational period of available data, i.e. up to 11 years of follow up. The Cox proportional hazards regression will take into account the fact that individual matching (1:1) will be performed by considering the exposed patient and his/her matched controls as one stratum and including this as a stratum in the Cox proportional hazards model. Additional variables will be included in the model if available. The cumulative incidence plots will be accompanied by number of patients at risk at different time points during follow-up. For (possibly) repeating events (such as exacerbation event) additionally a Poisson regression model will be fitted for the number of events (taking into account the matching). Time in the study will be included as an offset variable in the model. The cox and Poisson models will be adjusted for unbalanced PS-variables at baseline.

The outcome will be analyzed separately for each:

- 1) Primary outcome
 - Comparison of pneumonia incidence in COPD patients using LAMA and ICS/LABA
 - Comparison of exacerbations frequency and rate in COPD patients using LAMA and ICS/LABA : moderate or severe exacerbation

Proprietary confidential information © 2022 Boehringer Ingelheim International GmbH or one or more of its affiliated companies

[figure not shown]
- Comparison of time to start triple combination therapy (time from initial 'LAMA mono' or ICS+LABA' to 'LAMA+LABA+ICS' combination) in COPD patients using LAMA and ICS/LABA

2) Secondary outcome

- Comparison of all-cause mortality differences in COPD patients using LAMA and ICS/LABA
- Comparison of lung cancer incidence in COPD patients using LAMA and ICS/LABA
- Comparison of health care utilization: Medical cost / No. of prescriptions, visits and hospitalizations (hospitalization mainly due to severe exacerbation of COPD)

Health care utilization

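### Prior tuberculosis, which TB recurrence requires, is not named in the readable eligibility, matching or propensity-score text, so that hazard ratio is open to confounding by TB history or, if restricted after matching, to loss of most usable pairs

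*Combined protocol and SAP*

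**What the plan says.** TB recurrence is an objective on the title page, in the abstract and in section 8. Section 8 lists "cataracts and recurrence of tuberculosis, Non-tuberculosis Mycobacteria lung disease" among the expected events after long-term ICS use. The abstract reads "Expected adverse events after long term use of ICS : recurrence of TB and incidence of NTM lung disease". Setting recurrence of TB beside incidence of NTM disease indicates that the word is deliberate and does not simply mean new TB.

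The readable text on who enters, how patients are matched and what is adjusted for is as follows:

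- **Eligibility (9.2).** The only disease-history exclusion is "Patients with lung cancer, IPF, ILD or lung transplantation at the time of COPD diagnosis". TB is neither required nor excluded.
- **Matching factors (9.7.1).** Sex, plus "age category (5 year spans above 55 years), years since diagnosis of COPD, as available in the database, and propensity score".
- **Propensity score (abstract, 9.7, 9.7.1.1).** The score is "based on age, sex, socioeconomic status, Charlson Comorbidity Index, and asthma, and history of COPD exacerbation".
- **Balance and adjustment (9.7.1.1).** A standardised difference below 0.1 counts as success. Propensity-score variables above 0.1 are adjusted for. Further adjustment is allowed, but no variable is named.
- **Model (9.7, 9.7.2).** Hazard ratios come from a matched Cox model for all outcomes, stratified "by considering the exposed patient and his/her matched controls as one stratum".
- **Subgroups (9.7.1.1).** Matching is repeated because "covariate balance is not automatically maintained in sub-cohorts".

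**The concern.** A patient with no earlier TB has zero hazard of recurrence by definition. The at-risk set is therefore a subset of the cohort, marked by a variable that no readable step controls or checks. That leaves two simple ways to run the planned model, each with a weakness.

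If all matched patients are analysed, each arm's recurrence rate is proportional to its share of patients with prior TB. A difference in that share appears in the hazard ratio as if it were a drug effect, and the readable plan has no step that would detect it.

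If patients without prior TB are dropped from the existing pairs, a stratum is informative only when both members have prior TB. Most prior-TB patients would be discarded because their partner was not chosen on TB history.

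At stake is a stated safety comparison for ICS. It is not one of the readable primary or secondary endpoints.

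**Working it through.** **Inputs from the documents.** 1:1 matching (9.7.1.1); pair-stratified Cox (9.7.2); at least 5,000 patients per arm (9.5), so N = 5,000 pairs and 2 × 5,000 = 10,000 patients, which agrees with the stated total. The plan gives no precision calculation for TB recurrence that could be reproduced.

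**Assumed inputs.** Prior-TB share by arm, 5% to 20%; recurrence risk over follow-up in those with prior TB, 2% to 10%; TB history independent within pairs. The documents give no figure for any of these.

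**1. Whole matched cohort, no drug effect.** Recurrences in each arm are proportional to its prior-TB share, so the apparent HR is about p₁/p₀. Standardised difference = |p₁ − p₀| / √{[p₁(1 − p₁) + p₀(1 − p₀)]/2}.

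| Prior TB, two arms | Apparent HR (depends on which arm has more) | Standardised difference |
|---|---|---|
| 10% v 10% | 1.00 | 0 |
| 10% v 12% | 0.83 or 1.20 | 0.064 |
| 10% v 13.2% | 0.76 or 1.32 | 0.100 |
| 8% v 12% | 0.67 or 1.50 | 0.134 |
| 10% v 15% | 0.67 or 1.50 | 0.152 |

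A simulation of the pair-stratified comparison with a true HR of 1 (2,000,000 pairs) gave 1.50 at 10% v 15% and 0.98 at equal shares, which agrees with the formula. The third row matters: an imbalance right at the plan's 0.1 limit would still move this hazard ratio by about a third.

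**2. Restriction to prior TB within existing pairs.** Pairs with both members at risk = N·p₁·p₀. Prior-TB patients = N·(p₁ + p₀). Share lost = 1 − 2p₁p₀/(p₁ + p₀), which does not depend on N.

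| Prior TB, two arms | Both-TB pairs of 5,000 | Prior-TB patients | Share lost |
|---|---|---|---|
| 5% v 5% | 12.5 | 500 | 95% |
| 8% v 12% | 48 | 1,000 | 90% |
| 10% v 10% | 50 | 1,000 | 90% |
| 10% v 12% | 60 | 1,100 | 89% |
| 10% v 15% | 75 | 1,250 | 88% |
| 20% v 20% | 200 | 2,000 | 80% |

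For equal shares p and recurrence risk r, pairs with at least one recurrence = N·p²·[1 − (1 − r)²]. Across 5-20% and 2-10% this runs from 0.5 to 38. By the Schoenfeld formula (illustrative HR 1.5, two-sided 0.05), power is 3% to 24%.

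**3. Re-matching inside the prior-TB set.** The upper bound is N·p pairs: 250, 500 and 1,000 at 5%, 10% and 20%. Pairs with at least one recurrence run from about 10 to 190, and power for HR 1.5 from 9% to 80%. About 191 events are needed for 80%.

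**4. A larger cohort.** Section 9.5 gives about 200,000 COPD patients a year and 26% LAMA use: 200,000 × 0.26 = 52,000 users before the inhaler-naive and adherence filters. If 52,000 pairs could be matched, both-TB pairs would number 130 to 2,080 at 5% to 20%.

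**The case against.** The strongest reply is that the part of the protocol that would cover this outcome cannot be read. TB recurrence is absent from the readable outcome lists in 9.3.2 and 9.7.2. The contents page has blacked-out entries after 9.3.2.2 and between 9.7.2 and 9.8, and the ENCePP checklist cites a section 9.7.3 that is not visible. An at-risk set and TB-specific matching may be there. This stands, and it makes the point conditional.

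Second, the readable plan has provisions that could solve the problem. Section 9.7.1.1 repeats the matching for subgroup analyses, 9.7.1.1 and 9.7.2 allow further covariates, and 9.12 describes a broader score that takes in other comorbidities and drugs. This also stands in part: none of these provisions names TB or is tied to the recurrence outcome.

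Third, a reader might infer that the hazard ratio must be either confounded or based on very few pairs. The documents do not support that. Re-matching is a third route, equal TB shares would give no bias, and 5,000 per arm is described as a conservative minimum, so absolute pair counts could be much larger. A larger cohort would not, however, remove the whole-cohort bias or, under independent pairing, reduce the share of prior-TB patients lost.

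Fourth, a reader might infer that ICS would falsely appear protective because prescribers avoid it after TB. No section says so; section 7 says instead that ICS are widely overprescribed. The direction is unknown.

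**Conclusion.** The point holds as a conditional one. TB recurrence presupposes prior TB, and no readable eligibility, matching, propensity-score or automatic-adjustment rule takes account of it. Unless the blacked-out sections do, the comparison is exposed to confounding in the whole cohort, or to heavy loss of patients if restricted after matching.

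The size rests on assumed TB shares. Bias is nil at equal shares, a factor of about 1.2 in either direction at 10% v 12%, and 1.5 in either direction at 10% v 15%. Restriction within existing pairs loses 80-95% of prior-TB patients across shares of 5-20% if pairing is independent of TB history. The finding that few pairs remain applies at the planned minimum of 5,000 and need not hold in a much larger cohort. The documents establish neither that an imbalance exists nor that it favours one drug.

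The change is worth making: it is specific, it uses a rule the plan already contains, and it protects a stated safety comparison.

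**What to change.** - Add prior TB, defined as a TB diagnosis claim before the index prescription, to the main propensity score and the balance table.
- For TB recurrence, analyse only patients with prior TB. Re-estimate the score and re-match within that set under the subgroup rule of 9.7.1.1, and report numbers at risk per arm. Adding the covariate to the main score is not enough for this outcome, since an imbalance within the 0.1 limit can still matter.
- State the look-back window and its limit. The earliest look-back the protocol mentions is 2002, so older TB will be missed.
- If the blacked-out sections already define the at-risk set and its matching, align the propensity-score list and balance table with them.

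The cost is SAP wording, one covariate from the diagnosis codes listed in Annex 3, and one extra matched sub-cohort. The downsides are a smaller analysis set, a wider interval for this outcome, and some misclassification of TB history. At the minimum cohort size, precision may stay low even after re-matching.
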